## **5.0 Investigational Plan**

### **5.1 Overall Study Design and Plan: Description**

This is a Phase 1, open-label, dose escalation/Phase 2 randomized double-blind study of veliparib in combination with carboplatin and etoposide and maintenance veliparib monotherapy. Subjects in Phase 1 will be group sequentially assigned to the ascending dose levels of veliparib in combination with standard carboplatin/etoposide regimen based on the observed toxicities. Subjects in Phase 2 will be randomized in a 1:1:1 ratio to carboplatin, etoposide, placebo followed by placebo maintenance, or carboplatin, etoposide, veliparib followed by either veliparib or placebo maintenance. Approximately 215 adult male or female subjects diagnosed with extensive stage disease SCLC or other advanced/metastatic solid tumors will be selected to participate in the study according to the inclusion/exclusion criteria.

The study was designed to enroll approximately 35 subjects in Phase 1 and approximately 180 subjects in Phase 2 to meet scientific and regulatory objectives without enrolling an undue number of subjects in alignment with ethical considerations. Possible dose levels to be evaluated are as shown in [Table 4](#).

### **Phase 1 Dose Escalation**

The Phase 1 portion of this study will evaluate the safety, tolerability, dose limiting toxicities (DLTs), RPTD, pharmacokinetics (PK), and pharmacodynamics (PD) of veliparib in combination with carboplatin and etoposide in 21-day cycles in subjects with small cell lung cancer or advanced/metastatic solid tumors with possible schedules outlined in [Table 1](#), [Table 2](#) and [Table 3](#). For the Phase 1 subjects receiving non-continuous dosing, veliparib in Cycle 2 will be administered on Days 2 – 5 or Days 2 – 12 dependent on the dosing schedule to allow for evaluation of drug-drug interaction of veliparib with etoposide ([Table 2](#)). Details on drug administration and cycle schedules are described in Section [5.5.1.2](#).

**Table 1. Treatment Schema for Combination Therapy Cycles 1, 3, 4 in Phase 1 Dose Escalation (Non-Continuous Veliparib Dosing Schedules)**

Days	-2	-1	1	2	3	4 – 5 or 4 – 12	6 – 19 or 13 – 19
Veliparib	Twice a day						
Carboplatin			Once				
Etoposide			Once	Once	Once		

Note: Starting at Cycle 5 Day 1 veliparib dosed at 400 mg BID monotherapy continuous dosing for 21 days per cycle.

**Table 2. Treatment Schema for Combination Therapy Cycle 2 in Phase 1 Dose Escalation (Non-Continuous Veliparib Dosing Schedules)**

Days	-2	-1	1	2	3	4 – 5 or 4 – 12	6 – 19 or 13 – 19
Veliparib				Twice a day	Twice a day	Twice a day	
Carboplatin			Once				
Etoposide			Once	Once	Once		

**Table 3. Treatment Schema for Combination Therapy Cycles in Phase 1 Dose Escalation (Continuous Veliparib Dosing Schedule)**

Days	-2	-1	1	2	3	4 – 19
Veliparib	Twice a day					
Carboplatin			Once			
Etoposide			Once	Once	Once	

Note: Starting at Cycle 5 Day 1 veliparib dosed at 400 mg BID monotherapy continuous dosing for 21 days per cycle.

Upon completion of 4 cycles of combination therapy, subjects without evidence of disease progression will continue on maintenance monotherapy veliparib 400 mg BID until disease progression or unacceptable toxicity. Subjects who will be receiving prophylactic cranial irradiation (PCI) will have maintenance veliparib interrupted for the duration of radiotherapy as described in Section 5.2.3.2.

For subjects in the Phase 1 dose escalation portion of the study, each subject will participate in only 1 dose group and there is no provision for intra-subject dose-escalation. Study procedures are provided in the Schedule of Assessments and Pharmacokinetic and Pharmacodynamic tables (Section 5.3.1).

All subjects will be monitored for DLTs during DLT observation period (Cycle 1 Day –2 to pre-dose on Cycle 2 Day 1), and treatment-related adverse events (AEs) will be evaluated throughout the course of the study for evidence of acute, delayed, or cumulative toxicities.

Subjects who do not complete the DLT observation period for reasons other than DLT (e.g., withdraw consent, non-compliance, etc.) will be replaced to ensure appropriate number of subjects are evaluated.

The dose levels of veliparib to be evaluated in the dose-escalation portion of this study were determined based on the outcome of prior clinical studies of veliparib as well as on pre-clinical toxicology, toxicokinetic, and nonclinical anti-tumor efficacy studies. The following dose levels may be evaluated in the dose-escalation portion of the study: 80, 120, 160, 200 and 240 mg BID (Table 4). Reduced dose levels may be evaluated based upon review of subject safety and PK data. Intermediate dose levels may be evaluated based upon review of subject safety including, but not limited to, Grade 2 study-drug related AEs. If the MTD is not reached at veliparib 200 mg BID dose level, higher dose levels (with no more than 25% veliparib dose increments, and not exceeding single agent veliparib RPTD of 400 mg BID (Table 4, Levels V – VIII) or alternative veliparib dosing schedules may be evaluated at the discretion of the sponsor. The alternative dosing schedules can include dosing veliparib for Day –2 to Day 12 (14-day schedule) and/or Day –2 to Day 19 (continuous schedule) of the 21 day cycle (Table 1, Table 2 and Table 3). The initial dose for these schedules will be 200 mg BID or the maximum administered dose (MAD), not exceeding the MTD in the 7 day schedule. The 14-day schedule will be explored prior to continuous dosing schedule. Reduced or interim dose levels may be evaluated based on review of the safety and PK.

**Table 4. Phase 1 Dose Escalation**

Dose Level	Number of Subjects	Doses		
		Veliparib mg	Carboplatin AUC, mg/mL*min	Etoposide mg/m 
I	3 – 9	80	5	100
II	3 – 6	120	5	100
III	3 – 6	160	5	100
IV	3 – 6	200	5	100
V	3 – 6	240	5	100
VI	3 – 6	300	5	100
VII	3 – 6	340	5	100
VIII	3 – 6	400	5	100

A "3 + 3" escalation rule will be used for the dose-escalation portion of this study, with a condition applied for the Dose Level 1, which will allow 3 additional subjects to be entered in Dose Level 1 if 2 of 6 initial subjects experience DLTs. Enrollment of the 3 additional subjects at all dose levels will depend on a review of the specific DLTs observed and discussion with the Investigators.

A minimum of 3 evaluable subjects will be enrolled at each dose level. Additional eligible subjects may be enrolled at the current dose level at the discretion of the Investigators and the AbbVie TA MD. The dose escalation decisions will be made following the completion of the DLT observation period for the evaluable subjects in the intended cohort size. If a cohort is over-enrolled, reported toxicities in additional subjects will be taken into consideration.

**Dose-Escalation Criteria:**

AEs, clinical laboratory results and vital signs will be assessed throughout the study in each dose-escalation cohort.

DLTs will be assessed in each dose-escalation cohort during DLT observation period (Cycle 1 Day –2 to pre-dose Cycle 2 Day 1). Based on the safety and tolerability of study

drugs after the first cycle of treatment has been completed in at least 3 subjects, escalation to a subsequent dose level or expansion of the current dose level will occur based upon the following criteria (Table 5):

**Table 5. Dose Escalation Guidelines**

Number of Subjects with DLT in the First Cycle	Escalation Decision Rule
0 out of 3	Enter 3 subjects at the next dose level.
1 out of 3	Add 3 more subjects at current dose level. If AbbVie or the investigator considers the DLT(s) is clinically significant, AbbVie will determine if it is appropriate to add more patients at this dose level. 
 
• If < 2 of 6 subjects (or < 33% of subjects) experience DLT, dose escalation will proceed to the next dose level.
 
• If <math>\geq 2</math> of total 6 subjects (or <math>\geq 33\%</math> of subjects) experience DLTs, then dose escalation will be stopped.*
 

$\geq 2$ out of 3 or 6	Dose escalation will be stopped. *Additional subjects will be enrolled at the previous lower dose level as needed. The following exceptions apply to Dose Level 1: 
 
• If 2 of 6 initial subjects at Dose Level 1 experience DLTs, 3 additional subjects may be entered and the cohort will be expanded up to 9 subjects for further DLT assessment. 
 
○ Enrollment of the 3 additional subjects will depend on a review of the specific DLTs observed and discussion with the Investigators.
 
 
 
• If 2 of 9 subjects at Dose Level 1 experience DLTs, then escalation to the next dose level may proceed.
 
• If > 2 of 9 subjects in Dose Level 1 experience DLTs, dose-escalation will stop.
 

\* If 2 out of 6 subjects experience different DLTs, for example nausea and neutropenia, the data will be reviewed by the investigators and AbbVie to determine if 3 additional subjects should be added at that dose level. If 3 subjects will be added and none experience DLTs, this dose level will be declared the MTD.

An MTD and/or maximum administered dose (MAD), and RPTD, will be determined. The MTD is defined as the maximum dose at which < 2 of 6 or  $\leq 2$  of 9 subjects experience a DLT during the DLT observational period C1D-2 to C2D1. The MAD is defined as the highest dose tested. Both MAD and MTD may be determined independently for each tested dosing schedule of veliparib. The RPTD and schedule will be determined based on the assessment of the observed toxicities, the MTD or MAD, and

the overall safety profile of the study drug. The RPTD cannot exceed the lower of the MTD or MAD. At the RPTD and schedule additional subjects will be added as needed so that a total of at least 9 subjects will be treated at the RPTD.

DLT Definition: DLT is defined as any of the following drug-related toxicities occurring during the DLT observation period (Cycle 1 Day -2 to Cycle 2 Day 1) in any of the dose-escalation cohorts, with grading according to the National Cancer Institute (NCI) Common Toxicity Criteria for Adverse Events (CTCAE), version 4.0^20:

1. Cycle 1 events associated with treatment delay > 14 days in initiating Cycle 2 chemotherapy:
  - a. Grade 4 thrombocytopenia (platelets <  $25.0 \times 10^9/L$ )
  - b. Grade 4 neutropenia (absolute neutrophil count (ANC) <  $0.5 \times 10^9/L$ )
  - c. Grade 3 febrile neutropenia with fever lasting for > 7 days
  - d. Grade 4 febrile neutropenia of any duration

NOTE: Delay of more than 14 days in initiating Cycle 2 due to factors not directly related to treatment emergent toxicity will not be considered a DLT.

2. Grade  $\geq 3$  non-hematologic toxicity that represents at least 2 grade increase from baseline and is attributed to veliparib treatment:
  - a. Exclusion: nausea and vomiting lasting  $\leq 48$  hours or inadequately treated
  - b. Exclusion: electrolyte abnormalities resolving within  $\leq 24$  hours
  - c. Exclusion: hypersensitivity reactions
  - d. Exclusion: alopecia
3. Grade 2 non-hematologic toxicity that represents at least 2 grade increase from baseline, is attributed to veliparib treatment and requires a treatment delay of > 14 days in initiation of Cycle 2
4. Any toxicity that represents at least 2 grade increase from baseline, is attributed to veliparib treatment and requires at least one of:

- a. Dose modification within Cycle 1
- b. Omission of carboplatin, > 1 daily etoposide dose, or > 30% veliparib doses in Cycle 1

Subjects experiencing DLT(s) during the DLT observation period will require an interruption of study drugs and possible discontinuation from further participation in the study. Veliparib may be reintroduced at a reduced dose, if the toxicity returns to  $\leq$  Grade 1 or to baseline if Grade 2 at study entry. All decisions regarding continued dosing for individual subjects experiencing a DLT will be medically managed by the investigator in conjunction with the AbbVie TA MD.

A subject will be considered evaluable for DLT if he/she has completed the DLT evaluation period with the assigned regimen (full dose carboplatin, at least two doses of etoposide, with  $\geq$  80% compliance of veliparib) or discontinued Cycle 1 due to a DLT. All cohort sizes and numbers of subjects in the Phase 1 dose escalation criteria section above refer to evaluable subjects. Any subjects who discontinue from study prior to the completion of the DLT evaluation period for any reason other than a DLT will be replaced.

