**Safety:**

- The safety of veliparib in combination with carboplatin/etoposide will be assessed by evaluating the study drugs exposure, adverse events, serious adverse events, all deaths, as well as changes in laboratory determinations and vital sign parameters. Safety will be summarized per dose level using descriptive statistics for the dose escalation cohorts and per treatment arm in Phase 2.
- RPTD was determined based on the rate of DLTs and overall tolerability of the combination of veliparib, carboplatin and etoposide with at least 9 subjects treated at the RPTD in Phase 1 and will be further evaluated in Phase 2.

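### Phase 1 DLT evaluability does not fit DLT item 4b: a true DLT in a subject who resumes can drop out of the count, and veliparib omissions above 20% and up to 30% have no clear class

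*Protocol*

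**What the plan says.** All of this is in Protocol Section 5.1, below Table 5, unless stated.

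- **DLT item 4.** It opens "Any toxicity that represents at least 2 grade increase from baseline, is attributed to veliparib treatment and requires at least one of" and has two limbs. Limb 4a is "Dose modification within Cycle 1", a term that the protocol does not define. Limb 4b is "Omission of carboplatin, > 1 daily etoposide dose, or > 30% veliparib doses in Cycle 1".
- **Evaluability.** There are two routes. One is to complete the DLT period on the assigned regimen: full-dose carboplatin, two or more etoposide doses and at least 80% veliparib compliance. The other is to have discontinued Cycle 1 because of a DLT. The veliparib limit and the second route read "80% compliance of veliparib) or discontinued Cycle 1 due to a DLT".
- **Denominator.** "All cohort sizes and numbers of subjects in the Phase 1 dose escalation criteria section above refer to evaluable subjects".
- **After a DLT.** Section 5.1 calls for interruption and possible discontinuation, and permits reintroduction at a reduced dose. Section 6.8 says such subjects are generally discontinued but may continue with the sponsor's written approval.
- **Replacement.** One sentence in Section 5.1 covers subjects who do not complete the observation period for non-DLT reasons and names non-compliance as an example. The evaluability paragraph covers only those who leave the study early for a reason other than a DLT.
- **Compliance.** Section 5.5.7 also sets 80%, but allows the investigator to direct otherwise.
- **Use.** The Synopsis says the "RPTD was determined based on the rate of DLTs and overall tolerability of the combination".

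**The concern.** An evaluability rule should admit every subject who had the event being counted, and should not exclude subjects because they tolerated the dose poorly. This rule can do both.

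The first problem is a DLT that meets neither route to evaluability. The second is a band of veliparib omission that is too large for the 80% rule and too small for item 4b. The etoposide limits meet exactly: with three daily doses, omitting more than one means taking fewer than two. The veliparib limits do not meet, which suggests an oversight.

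At stake is the DLT rate behind the MTD and RPTD, a primary Phase 1 objective. Cohorts are 3 to 9 subjects, so one reclassified subject can change a decision.

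**Working it through.** **Step 1. Item 4b against the completion route**

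| Limb of 4b | Completion route requires | Can both hold? |
|---|---|---|
| carboplatin omitted | full-dose carboplatin | no |
| more than one etoposide dose omitted (at most 1 of 3 taken) | at least two taken | no |
| more than 30% of veliparib omitted (under 70% taken) | at least 80% taken | no |

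A 4b DLT is therefore evaluable only through discontinuation of Cycle 1. A subject who interrupts and resumes meets neither route.

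**Step 2. Direction of that error.** Let p be the true DLT rate and d the share of subjects whose DLT is dropped. The counted rate is (p − d)/(1 − d). It differs from p by −d(1 − p)/(1 − d), which is negative whenever d > 0 and p < 1. The error is downward under the protocol's own DLT definition.

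**Step 3. What one subject does** (Table 5 and the MTD definition, leaving aside the exceptions for Dose Level 1 and for differing DLTs):

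- Six subjects, two DLTs: 2/6 = 33.3%, escalation stops. Drop one DLT and add a subject without one: 1/6 = 16.7%, escalation proceeds.
- Nine subjects, three DLTs: 3/9 = 33.3%, outside the MTD definition. Make the same substitution: 2/9 = 22.2%, inside it.

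**Step 4. The omission band in whole doses.** Counting dosing days without a Day 0 reproduces the stated 7-day and 14-day schedules (Days −2 to 5 and −2 to 12). Days −2 to 19 give 21 days. At two doses a day, the band is every m of n with (n − m)/n < 0.80 and m/n ≤ 0.30.

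| Schedule | Doses n | Most missed, still evaluable | Band | Share missed in band | 4b starts at |
|---|---|---|---|---|---|
| 7-day | 14 | 2 | 3–4 | 21.4–28.6% | 5 (35.7%) |
| 14-day | 28 | 5 | 6–8 | 21.4–28.6% | 9 (32.1%) |
| continuous | 42 | 8 | 9–12 | 21.4–28.6% | 13 (31.0%) |

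The 14-day schedule is the one chosen for Phase 2.

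**Step 5. Direction for the band.** Let g be the share of subjects in the band who meet no other DLT item, and p the rate of all other DLTs. Neither is in the documents. Assume p = 20% and g = 10%:

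- kept as evaluable non-DLTs: p = 20.0%
- left out, as the text reads: p/(1 − g) = 0.20/0.90 = 22.2%
- counted as DLTs: p + g = 30.0%

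For p from 10% to 30% and g from 5% to 20%, the left-out rate is 0.5 to 7.5 points above the first classification and 3.4 to 17.5 points below the third. The exclusion has no fixed direction.

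**The case against.** **The dropped DLT is only a wording problem.** Table 5 counts subjects with a DLT in the first cycle, Section 6.8 says qualifying events will be considered DLTs, and both replacement sentences exclude DLT reasons. Nothing shows that a DLT was lost. This is fair as evidence of intent. But the denominator sentence limits all cohort numbers to evaluable subjects, and the evaluability sentence has no route for a DLT subject who resumes. The texts conflict, and the documents do not say how the counts were made.

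**The band is narrow.** This stands in part. DLT item 2 catches Grade 3 or higher "non-hematologic toxicity that represents at least 2 grade increase from baseline and is attributed to veliparib treatment", with listed exclusions and no omission threshold. Limb 4a catches Cycle 1 dose reductions for qualifying toxicity, and Table 17 pairs interruption with reduction for Grade 3/4 veliparib toxicity. What remains is mainly Grade 2 events, hematologic events without a delay beyond 14 days, and excluded events, with doses held and then resumed unreduced. If an interruption counts as a modification, 4a takes most of these too, but then the 30% limit in 4b has no function. Section 5.5.7 might excuse doses held on instruction, and Section 5.1 lets toxicities in over-enrolled subjects be considered. Neither is a counting rule.

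**Stronger readings.** A reader might infer that the band biases the DLT rate downwards and makes escalation too easy. That holds only if these subjects should count as DLTs, which the protocol does not say; under its own definition they are non-DLTs. A reader might also infer that the early review trigger in Section 8.1.9 is weakened because it uses the Phase 1 rate. A benchmark that is too low would make that trigger fire sooner. It concerned the first 15 Phase 2 subjects, and SAP Section 4.4 records that the safety DMC met in October 2017 and that no further review was thought necessary before database lock.

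**Conclusion.** The point holds in two parts of different strength.

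1. Read literally, the rules can remove a protocol-defined DLT from both numerator and denominator. That understates the DLT rate, and one subject is enough to change an escalation or MTD decision. This needs no assumption about rates, only that at least one 4b subject resumed instead of discontinuing Cycle 1.
2. Subjects who omit more than 20% and up to 30% of veliparib doses for toxicity, and meet no other DLT item, have no defined place. Their exclusion depends on tolerability, but its direction depends on how they should be classed. The figures in Step 5 are illustrations.

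The documents give no count of either kind, so the effect on the RPTD is unknown and may be nil. The RPTD also rested on overall tolerability.

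**What to change.** **Protocol.** Amend the evaluability paragraph in Section 5.1 so that any subject with a protocol-defined DLT is evaluable, whether or not Cycle 1 was discontinued. Reconcile the replacement sentences, DLT item 4 (including the undefined term in 4a), the evaluability paragraph and Section 5.5.7, so that toxicity-related shortfalls have one stated classification. Which classification is right is for the sponsor to settle. Making the band subjects evaluable without saying how they are classed would not settle it: as non-DLTs, they would lower the rate in Step 5 from 22.2% to 20.0%.

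**Phase 1 report** (SAP Section 4.2 places the Phase 1 analysis outside the SAP):

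- re-tabulate the cohorts with every DLT counted;
- list each non-evaluable or replaced subject with the reason;
- give the RPTD-cohort rate twice, with the band subjects as non-DLTs and as DLTs.

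If there were no such subjects, one sentence closes the matter.

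**Cost.** Protocol wording and one re-tabulation of data already held. The reported DLT rate may become slightly less favourable. No change to Section 8.1.9 is needed.

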### **Phase 1 Pharmacokinetics**

Pharmacokinetics of veliparib and etoposide will be assessed to determine the drug-drug interactions. Further pharmacokinetics of carboplatin will be assessed on Day 1 of Cycle 1 (please reference [Table 10](#) and [Table 11](#).)

### **Transition from Phase 1 to Phase 2**

Once the veliparib RPTD and schedule is determined, the veliparib RPTD and schedule will be communicated to all participating research sites prior to the start of enrollment into the Phase 2. Subjects from the Phase 1 Dose Escalation portion are not eligible for enrollment into the Phase 2 portion, but may continue to receive veliparib, carboplatin and etoposide at the assigned dose and schedule as long as they tolerate the study drug, show

no evidence of disease progression, and do not meet any of the criteria for subject discontinuation (Section 5.4.1).

### **Phase 2 Randomized Double-Blind**

The veliparib dose and schedule for the Phase 2 was determined to be 240 mg BID on a 14 day schedule based on the analysis of Phase 1 data.

Approximately 180 total subjects with treatment-naïve ED SCLC will be enrolled at the 240 mg BID veliparib/placebo dose and 14 day schedule in the Phase 2 double-blinded portion of the study. They will be randomized in a 1:1:1 ratio to one of three treatment arms:

Arm A: veliparib 240 mg in combination with carboplatin/etoposide followed by veliparib 400 mg BID monotherapy

Arm B: veliparib 240 mg in combination with carboplatin/etoposide followed by placebo monotherapy

Arm C: placebo in combination with carboplatin/etoposide followed by placebo monotherapy

Subjects in all Phase 2 study arms will receive a minimum of 4 cycles of combination therapy unless disease progression or unacceptable toxicity warrants earlier discontinuation from the treatment. Additional 2 cycles of combination therapy (e.g., up to a total of 6 cycles) may be administered at the investigators discretion if subject status at the completion of initial 4 cycles warrants continued combination treatment and/or if local SOC guidelines require 6 cycles of platinum-based therapy. In the combination cycles of Arms A and B, subjects will receive veliparib at 240 mg BID on a 14-day schedule, Arm C will receive matching placebo. After completion of the chemotherapy combination cycles (at least 4), subjects without evidence of disease progression will receive veliparib at 400 mg BID continuous dosing (21-day cycles) (Arms A), or

matching placebo (Arms B and C) as per treatment arm assignment, until disease progression or unacceptable toxicity occurs (Figure 2).

Subject randomization for Phase 2 will be stratified by baseline LDH level (> ULN versus ≤ ULN), and gender.

[figure not shown]
